- Pregnant participants will receive a 75-g oral glucose tolerance test during 24-28 gestational weeks, and GDM will be diagnosed if any of the following criteria are met, based on the recommendations of the International Association of the Diabetes and Pregnancy Study Groups Consensus Panel: fasting glucose ≥ 5.1 mmol/L, 1-hour glucose ≥ 10.0 mmol/L, or 2-hour glucose ≥ 8.5 mmol/L.
- Time Frame: during 24-28 gestational weeks.
- Type: binary variable (Yes / No).

(8) Maternal gestational weight gain (kg)

- This outcome will be calculated as body weight at delivery minus weight before pregnancy (self-reported).
- Time Frame: from pre pregnancy to delivery.
- Type: continuous variable.

(9) Maternal weight gain (kg) at early gestation

- This outcome will be calculated as body weight at around 20 gestational weeks minus weight before pregnancy (self-reported).
- Time Frame: from pre pregnancy to 20 gestational weeks.
- Type: continuous variable.

(10) Occurrence of gestational hypertension

- Pregnant participants will undergo blood pressure measurements at each prenatal visit. Gestational hypertension will be diagnosed if systolic blood pressure ≥ 140 and/or diastolic blood pressure ≥ 90 mmHg, based on the recommendations of the International Society for the Study of Hypertension in Pregnancy (ISSHP).
- Time Frame: during pregnancy.
- Type: binary variable (Yes / No).

- (11) Maternal body weight (kg) at 6 months after delivery (Continuous variable)
- (12) Maternal HbA1c (%) at 6 months after delivery (Continuous variable)
- (13) Infant body weight (g) at birth, 42 day, 3 months, and 6 months (Continuous, repeated measurements)
- (14) Infant length (cm) at birth, 42 day, 3 months, and 6 months (Continuous, repeated measurements)
- (15) Infant body mass index (kg/m²) at birth, 42 day, 3 months, and 6 months (Continuous, repeated measurements)
- (16) Medical cost that relates with fetus and birth defects during pregnancy and after birth (Time Frame: from confirmation of pregnancy to one year old after birth) (Continuous variable)

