3.3. Interventions

Experimental interventions: usual care plus additional procedures

- Before conception:

Participants will be examined for serum and RBC folate concentrations at enrollment to identify those with insufficient RBC folate concentration (<400ng/mL). Based on reviewing of folate supplement status of from the participant-administered questionnaire, a trained nurse will call the participant to inform them the RBC folate concentration and folate metabolism ability evaluated by one's genotypes of MTHFR C677T variant, and provide individualized folic acid supplementary instructions to improve folate status before get pregnant. A second RBC folate test is booked.

- During gestation -- Green channels for confirmation of fetus defects and a following genetic and clinical consulting:

In the both arms, fetus and infants with screen positive of fetus defect(s) will be referred via a green channel to approach an authorized tertiary obstetric hospital to achieve timely further routine comprehensive assessments and confirmative diagnosis. Then the participants with established diagnosis of fetus defects will be referred to a multi-discipline paediatric expert team for a deep consultation about possible postnatal treatments in the future to avoid unnecessary abortions.

- **After delivery:**

The participants from the experimental arm will additionally provide timely referral to a prespecified team of pediatrician experts for timely medical treatment or scheduled follow-up.

Standard tertiary interventions of birth defects (control arm, usual care):

Couples eligible for reproductive policy are entitled to routine health cares including general health cares (health education, medical history inquiry, physical examinations, consulting guidance and pregnancy outcome follow-up) and medical examinations (laboratory examinations, virus screenings and image examinations). But nutrients status is not included in these examinations, such as folate, vitamin B12 and microelements, etc. Regular antenatal cares are required, such as deformity screening by ultrasound. Routine neonatal screenings are conducted to diagnose infant with birth defect(s) timely.

Intervention procedures of FOID study

	Experimental arm Procedures in addition to the usual care	Control arm Usual care
Before conception		
Preconception at enrollment	RBC folate test Inform and instruction about folic acid supplementation via phone interview	Routine physical examination and routine blood tests

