7. TABLE CONTENTS

Table 1: Summary statistics of baseline information.

Variable	Statistics	Treatment A (N=)	Treatment B (N=)	All (N=)
Age (year)	n			
	Mean			
	SD			
	<35			
	≥35			
Ethnicity	n			
	Han			
	Other			
Preconception Body Mass Index, kg/m ²	n			
	Mean			
	SD			
	<24 kg/m ²			
	≥24 kg/m ²			
Parity, time	n			
	1			
	≥2			
Presence of adverse pregnant history	n			
	Yes			
	No			
Exposure to smoking	n			
	Yes			
	No			

Table 2: Summary statistics of compliance of participants.

Variable	Statistics	Treatment A (N=)	Treatment B (N=)	All (N=)
RBC folate concentration before pregnancy	n			
	Mean			
	SD			
	Median			
	IOR			
<400 ng/ml	n(%)			
≥400 ng/ml	n(%)			
RBC folate concentration at the first antenatal visit	n			
	Mean			
	SD			
	Median			
	IQR			
<400 ng/ml	n(%)			
≥400 ng/ml	n(%)			

Table 3: Summary statistics of primary and secondary outcomes estimated by GEE model.

Primary and secondary binary outcomes	N(%)		GEE model analysis	
	Treatment A (N=)	Treatment B (N=)	Risk Ratio (95%CI)	p-value
Occurrence of fetus defects, still birth, and birth defects				
Occurrence of fetal defects				
Occurrence of birth defects				
Occurrence of abortion that related with congenital defects				
Occurrence of gestational hypertension				
Occurrence of maternal gestational diabetes				

Table 4: Summary statistics of secondary repeated measured outcomes estimated by linear mixed model.

Secondary repeated measured outcomes	Visit	n, mean (SD)		Mixed model analysis		
		Treatment A (N=)	Treatment B (N=)	A vs. B Mean difference (95%CI)	p-value	P-value from Treatment*time interaction test
Baby body weight	Birth					
	42 days					
	3 months					
	6 months					
Maternal body weight during gestation	Periconception					
	Gestational week 20					
	At delivery					

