Appendix 2.2 Pregnant variable list in routine system

NO	variable	
	Basic information	
1	hospital card number	T
2	inpatient number	T
3	name	T
4	age	N
5	Pregnant times	N
6	Delivery times	N
7	last menstrual period	D
8	Gestational week at the first visit	N
9	The first visit date	D
10	Height	N
11	Weight	N
12	Systolic blood pressure at the first visit	N
13	Diastolic blood pressure at the first visit	N
14	Occupation	T
15	Education	T
	Antenatal care record	
16	Weight at each antenatal care	N
17	Systolic blood pressure at each antenatal care	N
18	Diastolic blood pressure at each antenatal care	N
19	Gestational week at each antenatal care	N
20	Antenatal care date	D
	Lab data	
21	Cytomegalovirus	N
22	Cytomegalovirus date	D
23	Rubella virus	N
24	Rubella virus date	D
25	Toxoplasmosis	N
26	Toxoplasmosis date	D
27	Syphilis screening	N
28	Syphilis screening date	D
29	Fasting blood-glucose	N
30	Fasting blood-glucose date	D
31	HCT(hematokrit)	N
32	HCT(hematokrit) date	D
33	Serum folate	N
34	Serum folate date	D
35	HCY(homocysteine)	N
36	HCY(homocysteine) date	D

37	OGTT 0 hours	N
38	OGTT 1 hours	N
39	OGTT 2 hours	N
40	OGTT date	D
41	Triglyceride	N
42	Triglyceride date	D
43	Total cholesterol	N
44	Total cholesterol date	D
45	Hemoglobin date	N
46	Hemoglobin date	D
	Delivery date	
47	Gestational week at delivery	N
48	Delivery mode	T
49	Birth weight	N
50	Birth weight(second baby)	N
51	Systolic blood pressure at delivery	N
52	Diastolic blood pressure at delivery	N
53	Apgar scoring	N
54	Delivery date	D
55	Birth defect records	T
56	Weight blood pressure at delivery	N

Note: The data will be extracted from maternal clinic antenatal medical record system.

T, text variable; D, The date type; N, Continuous variable; B, binary variable.

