Anthroposomatology		
93	Female height	N
94	Female weight	N
95	Female BMI	N
96	Female heart rate	N
97	Female SBP	N
98	Female SDP	N
99	Male height	N
100	Male weight	N
101	Male BMI	N
102	Male heart rate	N
103	Male SBP	N
104	Male SDP	N
Lab data		
105	Leucorrhea check	N
106	Clue cell	N
107	Monilia infection	N
108	Trichomomas	N
109	Cleanness	N
110	Whiff test	N
111	PH	N
112	Wom blood analysis	N
113	Female hb	N
114	Female wbc	N
115	Female rbc	N
116	Wom urine test	N
117	Female ABO	N
118	Female Rh	N
119	Female GLU	N

120	Female GLU levels	N
121	Female NG	N
122	Female chlamydia	N
123	Female syphilis	N
124	Female HIV	N
125	Female ALT	N
126	Female ALT levels	N
127	Female HBs-Ag	N
128	Female HBs-Ab	N
129	Female HBe-Ag	N
130	Female HBe-Ab	N
131	Female HBc-Ab	N
132	Female HCV-Ab	N
133	Female CMV IgM	N
134	Female CMV IgG	N
135	Female RV IgM	N
136	Female RV IgG	N
137	Female TOX IgM	N
138	Female TOX IgG	N
139	Male blood analysis	N
140	Male hb	N
141	Male wbc	N
142	Male rbc	N

Note: The data will be extracted the preconception care electronic data system T, text variable; D, The date type; N, Continuous variable; B, binary variable.

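### Both maternal weight-gain outcomes start from a self-reported weight and are analysed without adjustment, although a recorded preconception weight is available as a baseline covariate

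*SAP*

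**What the plan says.** **Outcome definitions (SAP 2.2.2).** Outcome (8): "This outcome will be calculated as body weight at delivery minus weight before pregnancy (self-reported". Outcome (9): "This outcome will be calculated as body weight at around 20 gestational weeks minus weight before pregnancy (self-reported". The time frame given for (9) drops the qualifier: "Time Frame: from pre pregnancy to 20 gestational weeks". There is no window and no rule for choosing among visits.

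**Analysis (SAP 5.2.2).** Continuous outcomes are analysed by a GEE with normal distribution and identity link, treatment as fixed effect and centre as cluster. No covariate is named. In the same section, repeatedly measured variables, with maternal weight in pregnancy as an example, get a linear mixed model that includes the baseline measurement as a covariate.

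**Weights collected (SAP Appendix 2).**
- Appendix 2.1, item 6, lists a female weight under the pre-pregnancy heading.
- Appendix 2.3, item 94, lists "Female weight" beside BMI, heart rate and blood pressure, drawn from the preconception care system.
- Appendix 2.2 lists the weight at each antenatal visit, the visit date and "Gestational week at each antenatal care".
- No variable is labelled as a self-reported pre-pregnancy weight.

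**Enrolment (SAP 3.3).** The procedures table places "Routine physical examination and routine blood tests" at preconception enrolment as usual care, and the experimental arm receives usual care plus additions.

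**Table 4 (SAP 7).** The rows for "Maternal body weight during gestation" are periconception, gestational week 20 and delivery. The source of the periconception weight is not given. Tables 3 and 4 have no row for the two gain outcomes.

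**The concern.** A gain score inherits all the error in its start value. Here the start value is the woman's own report, and the model contains nothing else that describes her body size before pregnancy. A preconception weight that was probably measured is already in the dataset. The SAP uses preconception BMI in Table 1, in the weighted analysis of the primary outcome and in its subgroups, and uses a baseline value in the mixed model for maternal weight. The gain outcomes get neither.

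What is at stake is precision, and protection against chance imbalance in body weight between arms formed from only 22 clusters. Two loose ends go with this. The SAP does not say which field supplies the pre-pregnancy weight for (8), (9) and Table 4. For (9), it does not say which antenatal weight counts as the week-20 weight.

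**Working it through.** The SAP states no SD, detectable difference or power for weight gain, so there is no figure to reproduce. Apart from the planned 1,100 per arm (SAP 3.5), every input below is an assumption.

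**1. Cost of error in the start weight.** If the error has SD e and is independent of the true gain (SD s), the variance inflation is (s² + e²)/s².

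| Assumed s | Reporting error e = 1.5 kg | Reporting error e = 3 kg |
|---|---|---|
| 5 kg, outcome (8) | (25 + 2.25)/25 = 1.09 | (25 + 9)/25 = 1.36 |
| 3.5 kg, outcome (9) | (12.25 + 2.25)/12.25 = 1.18 | (12.25 + 9)/12.25 = 1.73 |

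In terms of power, ignoring clustering, set the true difference to give 80% power without error. With s = 5 and e = 2, the SE rises by √(29/25) = 1.077 and power falls to 74%. Over s from 4 to 6 kg and e from 1 to 3 kg, the SE rises by 1% to 25% and power lies between 79% and 61%. These figures compare self-report with a perfect start weight, so they are not the gain from any available alternative.

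**2. The recorded weight as the start value.** It precedes conception by an unstated interval and so carries drift. The same formula with drift SD 1 to 2 kg gives 26/25 = 1.04 to 29/25 = 1.16 for (8), and 13.25/12.25 = 1.08 to 16.25/12.25 = 1.33 for (9). Drift of 2 kg is worse than reporting error of 1.5 kg (16% against 9%; 33% against 18%). Drift of 1 kg is better than reporting error of 3 kg (4% against 36%; 8% against 73%). Which start weight is better cannot be settled from the SAP.

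**3. The recorded weight as a covariate.** This needs no such choice. If r is the correlation between recorded weight and the gain outcome, the individual-level residual variance is multiplied by (1 − r²), which is never above 1. With an identity link the treatment coefficient remains a mean difference in kg. The value of r is not given, so the gain has no computable size. Adjustment removes the part of the gain, and of the reporting error, that varies with body weight. It does not remove purely random reporting error, which is why the sensitivity analysis is also needed.

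**4. The week-20 weight.** At an assumed 0.3 to 0.5 kg per week, a visit 1 to 4 weeks off target shifts a weight by at most 0.3 × 1 = 0.3 kg to 0.5 × 4 = 2.0 kg. If visits are spread evenly within ±w weeks, the SD is (weekly gain × w)/√3, or 0.17 to 1.15 kg. Gestational week and date are recorded at each visit, so a selection rule can limit this.

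**The case against.** The strongest reply is that the SAP never says the recorded weight was measured. Both appendix entries give only a numeric female weight. That stands: measurement is inferred from the neighbouring examination items and the routine physical examination. The reply adds that a report nearer to conception may be better than a clinic weight taken months before. That stands too (step 2 above), and it is why the recorded weight should not simply replace the self-report in the main analysis.

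A reader might go further and infer three things that the document does not support.

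- **Bias between arms from self-report.** The nurse's call in SAP 3.3 covers folate concentration, genotype and folic acid supplementation, not weight. SAP 3.4 says participants do not know the other arm's care. The SAP does not say when weight was self-reported, so the report may precede the call. Error independent of arm costs precision and does not bias the mean difference.
- **Bias from visit timing.** At 0.4 kg per week, a half-week difference between arms would be 0.2 kg. That is about one SE for (9) under an assumed ICC of 0.01: 3.5 × √(2/1100 × (1 + 99 × 0.01)) = 0.21 kg. But nothing suggests that timing differs, and SAP 3.1 says both arms follow the same clinical routines for outcome measurement.
- **Two conflicting weight-gain results.** Table 4 reports weights, not gains. Its silence on the source of the periconception row is not evidence of a second source.

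None of this bears on using the recorded weight as a covariate.

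**Conclusion.** The point holds as a minor improvement to two of sixteen secondary outcomes. The SAP collects a preconception weight, uses baseline adjustment in its model for maternal weight, and leaves it out of the two gain analyses. The benefit is precision. Its size depends on the correlation between recorded weight and gain, which the SAP does not give, and the illustrative SDs and error sizes are assumptions. The conclusion also assumes that the recorded weight belongs to enrolment, before the nurse's call, as the layout of SAP 3.3 and Appendix 2 suggests. The unnamed source of the start weight and the missing week-20 rule are gaps in detail to close in the same edit, not errors shown to alter a result.

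**What to change.** 1. In 5.2.2, add the recorded enrolment weight (Appendix 2.1 item 6 or Appendix 2.3 item 94, naming which) as a baseline covariate in the GEE for outcomes (8) and (9).
2. As a sensitivity analysis, repeat both outcomes with that recorded weight as the start value.
3. Name one variable as the pre-pregnancy weight, and use it in (8), (9) and the periconception row of Table 4.
4. For (9), use the dated antenatal weight nearest 20 weeks 0 days within a window fixed before unblinding, or interpolate where visits lie on both sides. An interpolated weight is an estimate and should be described as one.
5. Do not adjust for the interval from examination to last menstrual period. It is tempting as a correction for drift. But it arises after randomisation, and only the experimental arm is counselled to improve folate status before conceiving and booked for a second test. The intervention may therefore affect the interval, and adjustment could introduce bias.

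The cost is a few lines of SAP text and light programming. The recorded preconception and antenatal weights are already in the variable lists; the field holding the self-reported weight still has to be identified. The rules in 6.6 for missing baseline covariates can be extended to the recorded weight.

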2.2.3. Case ascertainment and case definitions

(1) Fetus and Birth defects

The examinations for detecting fetus and birth defects will follow the national routine usual care protocols. All fetus and birth defects identified from the 12 gestational weeks to 28 days after birth will be included. In consistent with the national birth defects surveillance policy, a total of 24 types of defects are defined (details of types of defects types see Appendix 1). Fetus defects will be detected by routine screening programs including prenatal DS screening, NT examination during gestational week 11 to 15, and ultrasound image examination during the second trimester (18-20 gestational week); and the number and type of birth defects after childbirth will be diagnosed and recorded according to national routine professional clinical examinations.

DS, caused by the trisomy, translocation, or partial trisomy of chromosome 21, is the most common genetic cause of intellectual disability. DS will be diagnosed by neonatologist. Neural tube defects including spina bifida and hypospadias, will be diagnosed by ultrasound examination and pediatric neurosurgeon.

CHD will be diagnosed by echocardiographic confirmation based on the local CHD screening policy (pulse oximetry plus cardiac murmurs). Hydrocephalus, digestive tract malformations, urinary malformations and other defects also will also be diagnosed either by ultrasound or some other specific diagnosis methods. From June 2016, a neonatal congenital heart defects screening policy has been issued in Shanghai city, the screening and diagnosis of CHD in neonates is embedded in this program following the routine protocols.

(2) *Abortion*

Abortion is defined as pregnancy suspension including miscarriage and artificial abortion. Detailed information for abortions will be collected, including time of abortion, reasons for abortion especially and antenatal information before abortion.

(3) *Pregnancy complications*

Pregnancy complications are a composite of gestational severe adverse events including maternal problems and fetal and placental problems. Maternal problems defined in this study include gestational diabetes, hyperemesis gravidarum, pelvic girdle pain, high blood pressure, deep vein thrombosis, anemia, infection, peripartum cardiomyopathy and hypothyroidism; Fetal and placental problems are defined as ectopic pregnancy, miscarriage, placental abruption, placenta praevia, placenta accrete, multiple pregnancies, vertically transmitted infection, intrauterine bleeding.

3. STUDY DESIGN

3.1. Design

This is a definitive, single-blind cluster randomized controlled - superiority trial embedded within the primary care system to assess the real-world effectiveness of a package of tertiary interventions before and during gestation in reducing the incidence of fetus and birth defects compared with the standard usual perinatal care. We will

recruit prepare-for-pregnancy women and their husbands through the pre-pregnancy eugenics examination clinic. Blood samples will be collected for examining RBC folate concentrations at enrollment. According to the randomization plan, participants recruited from the same community health care centre (cluster) will receive the same intervention, and clusters allocated to the two arms will receive the standard care or a serious experimental care procedure. The methods and protocols for measuring the primary outcome and the secondary outcomes in the two arms will follow the same clinical routines.

3.2. Trial Sites

The trial will recruit 22 community-based health care centers (clusters) where pre-pregnancy eugenics examination is facilitated in Shanghai: Jiuting, Fangsong, Yongfeng, Sheshan, Yueyang, Zhongshan, Xinbang, Xinqiao, Sijing, Yexie, Dongjing, Xiaokunshan, Qibao, Meilong, Pujiang, Hongqiao, Zhuanqiao, Jiangchuan, Wujing, Xinzhuang, Gumei and Maqiao community.

3.3. Interventions

Experimental interventions: usual care plus additional procedures

- Before conception:

Participants will be examined for serum and RBC folate concentrations at enrollment to identify those with insufficient RBC folate concentration (<400ng/mL). Based on reviewing of folate supplement status of from the participant-administered questionnaire, a trained nurse will call the participant to inform them the RBC folate concentration and folate metabolism ability evaluated by one's genotypes of MTHFR C677T variant, and provide individualized folic acid supplementary instructions to improve folate status before get pregnant. A second RBC folate test is booked.

- During gestation -- Green channels for confirmation of fetus defects and a following genetic and clinical consulting:

In the both arms, fetus and infants with screen positive of fetus defect(s) will be referred via a green channel to approach an authorized tertiary obstetric hospital to achieve timely further routine comprehensive assessments and confirmative diagnosis. Then the participants with established diagnosis of fetus defects will be referred to a multi-discipline paediatric expert team for a deep consultation about possible postnatal treatments in the future to avoid unnecessary abortions.

- **After delivery:**

The participants from the experimental arm will additionally provide timely referral to a prespecified team of pediatrician experts for timely medical treatment or scheduled follow-up.

Standard tertiary interventions of birth defects (control arm, usual care):

Couples eligible for reproductive policy are entitled to routine health cares including general health cares (health education, medical history inquiry, physical examinations, consulting guidance and pregnancy outcome follow-up) and medical examinations (laboratory examinations, virus screenings and image examinations). But nutrients status is not included in these examinations, such as folate, vitamin B12 and microelements, etc. Regular antenatal cares are required, such as deformity screening by ultrasound. Routine neonatal screenings are conducted to diagnose infant with birth defect(s) timely.

Intervention procedures of FOID study

	Experimental arm Procedures in addition to the usual care	Control arm Usual care
Before conception		
Preconception at enrollment	RBC folate test Inform and instruction about folic acid supplementation via phone interview	Routine physical examination and routine blood tests
During gestation		

1 st antenatal visit	RBC folate test	Routine clinical examinations
15 gestational weeks		Neuro-tube defects screening
18-20 gestational week	Provided clinical and genetic consulting regarding the identified defects provided by a prespecified team of fetus and pediatrician experts	Ultrasound screen for fetus defects, referred for further confirmation diagnosis
24 gestational weeks	NO	OGTT test for screening gestational diabetes
Late gestation about 35 gestational weeks	NO	Blood test Blood routines Kidney and liver function
After delivery		
Birth	+ Neonatal CHD screening followed by ECHO for congenital heart defects diagnosis + Refer to surgery or scheduled follow-up	Recorded observed defects

